A total of 330 Asian American breast cancer survivors will be recruited. Because information is limited on which to base power analyses, estimates are based on a two-sided Mann-Whitney test (assuming a uniform distribution) using an estimated effect size equal to 1/2 of a standard deviation, as suggested in the literature. In addition to being clinically meaningful, large effect sizes demonstrated in PS4 suggest that 0.5*SD is a statistically meaningful effect size to assume. Sample size is based on 80% power, and a type I error rate equal to 0.00625 to account for eight primary outcome measures modeled within the two primary aims (group main effects). Accordingly, group sample sizes of 105 each achieve 80% power to detect a difference of 0.5*SD between group means overall in a single follow-up period. The primary analysis will be an assessment of differences by intervention group in changes from baseline to Time Point 1, or one month post intervention. A secondary analysis will include similar modeling for sustainability of

intervention effects, or for changes from baseline to Time Point 2. Assuming an attrition rate of 35% by the Time Point 2, 330 Asian American breast cancer survivors would be an adequate number for the study with multiple outcomes. Considering the attrition rates reported in the literature^{66–68} and in PSs, the assumption of a 35% attrition rate is reasonable.

At the completion of their participation, the participants will be reimbursed with \$50 electronic gift cards for their participation. The reimbursement will be prorated. The participants will be allowed to choose "do not want to respond", which will NOT be considered missing data. The amount was determined based on preliminary studies.

o Description of recruitment materials and their use

Sample study announcement, sample study announcement in flyer format, and flyer for TICAA recruitment will be distributed through and displayed on cancer support groups and communities/groups for Asian Americans.

o Describe the procedures for data collection

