Components. The TICAA has three components in four languages (English, Mandarin Chinese, Korean, and Japanese): (a) social media sites; (b) interactive online educational sessions; and (c) online resources. To incorporate cultural differences among three different sub-ethnic groups, three separate social media sites are designed for each sub-ethnic group. The sites provide a mechanism by which participants can connect to each other and share their own breast cancer survivor experiences with peers, have interactions with and get support from peers, and receive coaching/support from culturally matched peers and health care providers.⁷⁷ In each site, cultural tailoring will be done through incorporating both general and sub-ethnicity-specific materials to discuss and culturally appropriate examples from PSs. The sites will incorporate Asian cultural values related to family (e.g., family as the center of the women's daily life) and the collectivistic values for Asian women as a way to frame discussions and to present content. Each site consists of a social media function (like the timeline of Facebook), a chat function with a culturally matched bilingual interventionist and a symptom log function. Interventionists are required to have a bachelor's degree in a health-related field and be bilingual. We will have a registered nurse (RN) monitoring or supervising the coaching/support provided by the interventionists. The RN will provide consultation to the interventionists while consulting with two MD consultants. For the intervention period, weekly group and individual coaching/support by culturally matched bilingual interventionists will be provided. Group coaching/support through the social media function will not have time limits because it will be based on asynchronous interactions. Yet, real-time and personalized individual coaching/support will be provided in a specific designated time period (each participant sets a specific time period for getting individual coaching/support) by the chat function. In addition, the use of phone calls and mobile chat functions (e.g., Wechat, Line, KaKao Talk, Skype et. al) as supplementary methods for individual coaching/support is permitted for the study-related communications. Group coaching/support will start once the first 10 women per sub-ethnic group are enrolled, but individual coaching/support will start as soon as a participant is enrolled. Starting the group coaching/support with 10 women is reasonable when considering that 10~30 are usually an adequate number for a focus group, and group cohesiveness needs to be established. 78 Each week, the interventionists will post at least 5 group messages related to each topic to give group coaching/support, and send at least 1~2 message(s) to each participant for individual coaching/support. Coaching/ support will focus on enhancing breast cancer survivorship by changing cultural attitudes, building self-efficacy, minimizing perceived barriers, and enhancing social influences through multiple ways (see Table 1). Messages in other languages will be translated into English, and those in English will be translated into other languages (using both Google translator and daily reviews/corrections by the bilingual interventionists with consultation of professional translators). The interventionists will minimally interfere the interactions among the participants.

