Aim #1: Effects on Primary Outcomes. Separate intent-to-treat general linear models 86 will be used to examine differences in continuous outcome measures by intervention group at each time point, adjusting for baseline outcome and any variables that demonstrate imbalances in preliminary analyses. Model assumptions will be assessed, and modifications will be implemented as necessary to improve mode fit. Differences in continuous outcome measures over time will be examined using an intent-to-treat linear mixed-model growth curve analysis with SAS Proc Mixed.86 Mixed models will be used in which all available data collected during follow-up is used.87,88 Separate mixed effects regression models will be generated for each outcome measure. Both random slopes and intercepts will be modeled to represent the subject level deviation from the average, or fixed-effect, slope over time and intercept, respectively. Restricted maximum likelihood estimation will be used, and the most appropriate covariance structure will be examined. The outcomes will be analyzed as repeated observations of the dependent variables, with mean-centered baseline outcome scores serving as a covariate. Other predictors will include intervention group, time from baseline to follow-up, the interaction of group and time, and the interaction of baseline measures and time. Baseline outcome and group will be analyzed as time-independent covariates. Other demographic or treatment timeindependent variables identified in preliminary analyses may be included as covariates. Main effects and higher order interaction terms will be examined. The Akaike information criterion will evaluate overall model fit and to select the best-fitting longitudinal change pattern.89

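### TICAA is delivered through shared sub-ethnic sites in one arm only, but the 80% power and the Aim 1 models treat women as independent and do not commit to the sub-ethnic quota factor

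*Combined protocol and SAP*

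**What the plan says.** **Delivery.** The Components paragraph of the intervention section says that "weekly group and individual coaching/support by culturally matched bilingual interventionists will be provided", and that "three separate social media sites are designed for each sub-ethnic group". Read literally, the second phrase could mean nine sites; the context supports one per sub-ethnic group, three in all. Women on a site exchange experiences with peers. Group coaching waits until ten women per sub-ethnic group are enrolled, partly so that the group can cohere. The Study Design section lists three interventionists. The same intervention section gives controls only the American Cancer Society material and sets a target of 55 women per sub-ethnic group in each arm of 165.

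**Sample size (under Recruitment).** The plan uses a two-sided Mann-Whitney test under a uniform distribution, with "a type I error rate equal to 0.00625 to account for eight primary outcome measures", and concludes that "group sample sizes of 105 each achieve 80% power to detect a difference of 0.5*SD between group means overall in a single follow-up period". It gives no intraclass correlation (ICC) or design effect. The total of 330 allows for 35% attrition by Time Point 2.

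**Analysis (Aim #1).** The general linear models adjust for baseline outcome and for variables found to be imbalanced. In the mixed model, "Both random slopes and intercepts will be modeled to represent the subject level deviation". No term for site, interventionist or sub-ethnic group is named.

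**The concern.** Peer influence and group coaching are active ingredients of TICAA, and social influences are a hypothesised mediator under Aim 2. Outcomes of women who share a site, a discussion group or an interventionist may therefore be correlated. This can happen in the TICAA arm only. Similarity due to sub-ethnicity alone is a different matter: the quota balances it across arms, and it does not by itself lower power.

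Two things are at stake. First, the 80% is presented without the condition on which it rests. Second, the factor that defines both the quota and the sites may never enter the primary model. Because the quota balances it, the imbalance rule would not normally select it.

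**Working it through.** **Inputs.** From the sample-size paragraph: difference 0.5 SD, two-sided alpha 0.05/8 = 0.00625, 105 per arm. From the intervention section: three sites, so 105/3 = 35 women per site, or 165/3 = 55 with full enrolment. Assumed, because the documents give none: ICC 0.01, 0.02, 0.05.

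**1. The plan's figure.** For a uniform distribution the Mann-Whitney test has asymptotic efficiency 1.0 relative to the t test, so the t calculation applies. The noncentrality is 0.5 × √(105/2) = 3.623 on 208 degrees of freedom. Power is 80.4% at 105 per arm and 79.9% at 104, so 105 reproduces. (Directly simulating the Mann-Whitney test on two shifted uniforms gives about 75%. That is a separate matter; the plan's number matches the usual efficiency-based formula.) For attrition, 330 × 0.65 = 214.5, which covers 210.

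**2. Correlation in one arm.** With m women per correlated group:

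- design effect DE = 1 + (m − 1) × ICC
- variance of the difference = SD² × (DE + 1)/n
- standard error (SE) ratio = √((DE + 1)/2)
- noncentrality = 3.623 / SE ratio at n = 105, or 0.5 × √(165/2) = 4.542 / SE ratio at n = 165

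| Setting | ICC | DE | SE ratio | Power |
|---|---|---|---|---|
| 105 per arm, m = 35, sites random | 0.01 | 1.34 | 1.08 | 72.1% |
| | 0.02 | 1.68 | 1.16 | 64.3% |
| | 0.05 | 2.70 | 1.36 | 46.2% |
| 105 per arm, groups of 10 | 0.01 | 1.09 | 1.02 | 78% |
| | 0.02 | 1.18 | 1.04 | 76% |
| | 0.05 | 1.45 | 1.11 | 69% |
| 165 per arm, m = 55, sites random | 0.01 | 1.54 | 1.13 | 90% |
| | 0.02 | 2.08 | 1.24 | 82% |
| | 0.05 | 3.70 | 1.53 | 58% |

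These rows assume a test that uses the correct standard error and many degrees of freedom.

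**3. Slack.** On the normal approximation (81.3% at 105 per arm with ICC 0), power falls below 80% once the ICC with 35 per site exceeds about 0.0016. At 107 per arm the figure is about 0.0026.

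**4. Sites held fixed.** If inference concerns these three sites only, their mean differences are not sampling error. With equal site sizes the variance of the difference is SD² × ((1 − ICC) + 1)/105. The SE is √(1.99/105), √(1.98/105) and √(1.95/105), that is 0.138, 0.137 and 0.136 SD, against √(2/105) = 0.138 at ICC 0. Simulation with site effects held fixed agrees: SE about 0.137 and power about 81% to 83%.

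**5. Sites as a random effect.** With three sites, Satterthwaite degrees of freedom are about 6, 5 and 4, and power at 105 per arm falls to about 36%, 26% and 12%, so this model is not workable. Ignoring random sites gives a type I error per outcome of 2 × [1 − Φ(2.734 / SE ratio)] = 0.0115, 0.018 and 0.044. Sub-ethnic-by-arm fixed terms do not cure this: with them in the model, simulated error stays at about 0.011 to 0.048.

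**6. Value of the quota factor.** If sub-ethnic group explained an assumed 10% of outcome variance, including it would raise the standardised effect to 0.5/√0.9 = 0.527. Power at 105 per arm would rise from about 82% without the factor to about 85% with it.

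**The case against.** The strongest reply is that a random-site power loss and a fixed-site analysis answer different questions. That stands. A reader might infer that the standard error is too small whenever sites differ, or that the trial really has 46% to 72% power. The documents support neither. They give no ICC, and in the TICAA arm each site coincides with one sub-ethnic group, so a site effect cannot be separated from a sub-ethnic difference in treatment effect. For inference about these sites, step 4 shows no inflation.

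Three further points have weight:

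- Thirty-five per site is an upper bound on the correlated group. The plan reports 210 women finished before the remaining 120 are recruited, and much of the coaching is individual.
- The 35% attrition is by Time Point 2, whereas the primary comparison is at Time Point 1. Aim 1 also adjusts for baseline. With an assumed baseline correlation of 0.5, the noncentrality at 105 per arm is divided by √0.75, and random-site power is about 86% and 80% at ICC 0.01 and 0.02. The sample-size paragraph claims neither gain.
- Aim 1 allows demographic covariates and higher-order interactions, and Aim 3 explores background factors as moderators. This coverage is partial: sub-ethnic group is neither named nor committed to in the primary model.

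**Conclusion.** The concern holds in a limited form. The 80% is correct under independence, has almost no slack at 105 per arm, and is stated without that condition although one arm is delivered in groups. The possible loss depends on an ICC that must be assumed and on the inference intended. It is about 72%, 64% or 46% power at ICC 0.01, 0.02 or 0.05 if the claim extends beyond these sites, and about 78%, 76% or 69% if the correlation lies within groups of about 10 women. With fixed sites and no correlation inside a site, there is no loss. It would be wrong to conclude that the trial is underpowered, or that adding sub-ethnic terms recovers power for a wider claim. The missing commitment to the quota factor does not depend on any ICC.

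**What to change.** 1. In the sample-size paragraph, state that the 80% assumes no correlation from shared delivery. Give the sensitivity range, with the random-site figures labelled as applying only to inference beyond these sites.
2. In the Aim 1 models, include sub-ethnic group and sub-ethnic-by-arm fixed terms (2 + 2 = 4 terms). Take the equally weighted average of the three arm effects as the primary contrast, and let residual variance differ by arm.
3. State that inference applies to these three sites and interventionists, and that the added terms do not correct for peer or cohort correlation within a site.

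The cost is plan wording, a few degrees of freedom, a less favourable power statement and a narrower claim. No extra recruitment is needed.

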A technology-based approach using computers and mobile devices (smart phones and tablets) promises to meet this necessity with high flexibility and accessibility, and minimizes the cost of the intervention in busy health care settings. Also, a technology-based intervention that does not involve face-to-face interactions could work better for many women from cultures where breast cancer is still a stigmatizing experience. Bespite the high potential, few technology-based interventions are available for ethnic minority breast cancer survivors, especially for Asian Americans. Therefore, based on Preliminary Studies (PSs), the research team has developed and pilot-tested a theory-driven technology-based information and coaching/support program that: (a) is tailored to Asian American breast cancer survivors by incorporating actual data on individual sub-ethnic groups cultural attitudes from PSs; (b) uses multiple languages; (c) provides both group and individual (real-time and personalized) coaching/support by culturally matched bilingual health care providers; (d) incorporates peer support through a social media function; and (e) integrates existing general and culture-specific evidence-based educational content from scientific authorities. Among over 71 sub-ethnic

groups of Asian Americans,⁴⁶ only three sub-ethnic groups (Chinese, Korean, and Japanese) were selected for the program development for the convenience of the approach (e.g., language). Within Asian Americans, Chinese are the largest sub-ethnic group,^{47,48} Koreans are the fastest growing sub-ethnic group,^{47,48} and Japanese are the sub-ethnic group at the highest risk of breast cancer.^{1,2,11,49}

Goals/Aims

The purpose of the proposed randomized intervention study is to test the efficacy of the technology-based information and coaching/support program for Asian American breast cancer survivors (TICAA) in enhancing the women's breast cancer survivorship experience.

The **specific aims** of the study are to:

Aim 1. Determine whether the intervention group (who uses the TICAA and the information on breast cancer by the American Cancer Society [ACS]) will show significantly greater improvements than the control group (who uses only the information on breast cancer by the ACS) in **primary outcomes** of the TICAA (needs for help, physical and psychological symptoms, and quality of life) from baseline (pre-test) to Time Points 1 (post 1-month; primary) and 2 (post 3-months; secondary).

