The data are mainly collected through the Internet survey questionnaire. When potential participants visit the project Web site (after receiving/reviewing a study announcement), they will be asked to review the informed consent. When participants click I agree to participate, they will have given their consent. Then, after checking them against the inclusion criteria and quota requirements, only those who meet the criteria and requirements will be automatically assigned a serial number, and randomized into two groups using an automated random number generator accessible through the Web site.

Then, the women will be asked to fill out the Internet survey questionnaire (if requested, paper-and-pencil questionnaires will be provided/used, or research staff will assist in administering the Internet surveys over the phone.) and sign up the Web site by creating their own ID and passwords. Whenever they visit the Web site, they need to use the ID and passwords to log in the site. If they want, they can change their ID and passwords. Then, both groups will be provided with an electronic instruction sheet on when they need to come back and fill out additional questionnaires and/or use the program.

Biweekly, the research team will send reminders and thank-you emails. Two weeks before the end of the 1st month, both groups will be asked to fill out the next set of the instruments by the end of the 1st month. Then, 2 weeks before the end of the 3rd month, both groups will be asked to fill out the next set of the instruments by the end of the 3rd month.

O Description of research instruments to be used (e.g., questionnaires, surveys, interview or focus group guides, scales)

Multiple instruments will be used: the Support Care Needs Survey-34 Short Form (SCNS-34SF),⁵⁰ the Memorial Symptom Assessment Scale-Short Form (MSAS-SF),⁵¹ the Functional Assessment of Cancer Therapy Scale-Breast Cancer (FACT-B),⁵² the modified Questions on Attitudes, Self-Efficacy, Perceived Barriers, and Social Influences (QASPS),⁵³ the Cancer Behavior Inventory (CBI),^{54,55,56} the Perceived Isolation Scale (PIS),^{57,58} the Personal Resource Questionnaire (PRQ-2000),⁵⁹ and 27 questions on background characteristics, level of acculturation, and disease factors. The reliability and validity of all the instruments have been established among Asian Americans. Cronbach's alpha of individual instrument ranged from .76 to .96 among Asian Americans.

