Data analysis will be conducted at Emory University, School of Nursing. Data collected through the Internet will remain confidential unless a participant appears at risk of harm. Only the research team will have access to the study records, which will be directly saved in a computer file format called ASCII. No individual identities will be used in any reports or publications that will result from this study.

Preliminary Analysis & Missing Data. Serial ID numbers will be assigned and attached to the data. Descriptive statistics will be used to characterize all variables, and distributions of variables will be examined for outliers and normality. Then, transformations will be applied as appropriate. Internal consistency reliability estimates for multi-item scales of at least 0.7 will be considered acceptable. We will use an intent-to-treat approach; participants will be analyzed in their original randomized conditions regardless of the usages of the TICAA or follow-ups missed. The mechanism underlying missing data will be evaluated and appropriate imputation methodology will be implemented (e.g., missing at random and multiple imputation by chained equations).84 All enrolled patients with at least one follow-up assessment will be included in outcome modeling, and the linear mixed effects modeling will take advantage of all available data. Baseline characteristics will be compared among patients with and without complete follow-up. To assess potential biases, a comparison of withdrawal rates will be included. 84 If the number of participants dropping out is small (10%) and the missing observations can be considered random, then the primary hypotheses will be tested using the complete observed data. If missing observations cannot be assumed to be random, more complex approaches (e.g., shared parameter models85) will be considered.

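### Aim 1's growth model asks two follow-ups for a random intercept and a random slope, and no sentence names the model and term for the month-1 test

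*Combined protocol and SAP*

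**What the plan says.** Goals/Aims sets the comparison "from baseline (pre-test) to Time Points 1 (post 1-month; primary) and 2 (post 3-months; secondary". The sample-size paragraph under Recruitment repeats it: "The primary analysis will be an assessment of differences by intervention group in changes from baseline to Time Point 1". That paragraph sets the type I error at 0.00625 "to account for eight primary outcome measures modeled within the two primary aims (group main effects", and names no model for the primary analysis.

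Aim #1 (Effects on Primary Outcomes) then gives two models:

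- General linear models for "differences in continuous outcome measures by intervention group at each time point, adjusting for baseline outcome", also adjusting for any variables found to be imbalanced.
- A mixed-model growth curve for differences over time. Baseline enters as a mean-centred covariate. The predictors include group, time since baseline, group-by-time and baseline-by-time. On random effects: "Both random slopes and intercepts will be modeled to represent the subject level deviation from the average". The covariance structure is to be examined, AIC is named, and other covariates are optional.

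The missing-data paragraph says "All enrolled patients with at least one follow-up assessment will be included in outcome modeling" and points to linear mixed modelling. Aim #3 reuses the mixed model, adds random slopes for moderators to account for variability within individuals, and reads the intercept as the mean baseline score.

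**The concern.** With baseline on the right-hand side, each woman contributes at most two responses. Two time points give little or no means of separating woman-to-woman variation in slope from residual error, yet representing that variation is the stated purpose of the random effects. Convergence or boundary problems could then arise in some of the eight outcome models, and any reduced structure would be chosen after seeing the data, from candidates that the plan does not list.

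The second issue bears more directly on the result. A trial with eight tests at 0.00625 should say which model and which coefficient supply each test. In the linear model the group coefficient is the month-1 difference. In the growth model, with time counted from baseline and a group-by-time term present, the group coefficient is the fitted difference at month 0. An analyst who takes the sample-size paragraph literally and reads the group line of the mixed-model output would test the wrong quantity.

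**Working it through.** **Inputs.** From the documents: responses at months 1 and 3; 330 women; 35% attrition by month 3; 105 evaluable per arm; 0.5 SD effect; two-sided 0.00625; questionnaires requested two weeks ahead ("Two weeks before the end of the 1st month, both groups will be asked to fill out the next set of the instruments", and likewise for month 3). Assumed, because the documents do not give them: equal residual variances of 1 at the two visits, and a residual correlation rho of 0.3, 0.5 or 0.7.

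**The plan's own figure.** 0.05/8 = 0.00625, critical value 2.734. With 105 per arm, SE = sqrt(2/105) = 0.138 SD and 0.5/0.138 = 3.62. Power is 81% by the normal approximation and 80% by the noncentral t, treating the Mann-Whitney test as equivalent to a t test. So 105 is reproduced. 210/0.65 = 323, which 330 covers.

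**Parameter count.** Let g00 and g11 be the intercept and slope variances, g01 their covariance and s2 the residual. At t = 1 and 3:

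- V11 = g00 + 2·g01 + g11 + s2
- V12 = g00 + 4·g01 + 3·g11
- V22 = g00 + 6·g01 + 9·g11 + s2

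That is three equations in four unknowns (rank 3). For example, (g00, g01, g11, s2) = (1.25, -0.30, 0.18, 0) and (0.50, 0, 0.03, 0.30) both give V11 = 0.83, V12 = 0.59, V22 = 1.07. With equal variances, g11 = (1 - rho - s2)/2, so every slope variance from 0 to 0.35, 0.25 or 0.15 (rho 0.3, 0.5, 0.7) fits identically.

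Setting g01 = 0 leaves three unknowns for three moments, with g11 = (V22 - V11)/8. That is identified, but with nothing left over to check it.

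**Actual completion dates as time.** Assume completion spread evenly over each two-week window, 330 women at month 1 and 214 at month 3. The correlated version is then identified, but SE(g11) is about 0.15, 0.12 or 0.07. The 95% interval widths (2 × 1.96 × SE) are about 0.60, 0.46 and 0.29, each wider than the whole range above.

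**Effect on the month-1 contrast.** None. In one simulated complete dataset of 210 women, three REML starts reached the same likelihood with slope variances of 0.000, 0.009 and 0.004. Each gave a month-1 difference of 0.639 (SE 0.111), the same as the baseline-adjusted linear model. The growth model's group coefficient in those fits was 0.843 (SE 0.147).

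**What the group coefficient tests.** With group differences d1 and d3 at months 1 and 3, the line through them at month 0 is 1.5·d1 - 0.5·d3. Its SE is 0.138 × sqrt(2.25 + 0.25 - 1.5·rho). With d1 = d3 = 0.5 SD and 105 per arm (noncentral t):

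| rho | SE | Power, group coefficient | Power, month-1 contrast |
|---|---|---|---|
| 0.3 | 0.198 | 41% | 80% |
| 0.5 | 0.183 | 49% | 80% |
| 0.7 | 0.166 | 60% | 80% |

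If the effect fades, the coefficient exceeds the month-1 difference: d1 = 0.5 and d3 = 0.25 give 0.625. Power is then higher than in the table, but for a quantity that nobody observed.

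**Linear model against mixed model for the same month-1 contrast.** They agree exactly if no woman is seen only at month 3. If 5 to 10% are (assumed) and month 1 is not imputed, simulation puts the two on different sides of 0.00625 in 0.5 to 2% of tests at 0.5 SD and 2 to 8% at 0.35 SD.

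**Aim 3.** Random intercept, time slope and one moderator slope, with all covariances and a residual, make 7 parameters. The rank is 5 for a two-level moderator and 6 for a continuous one. A factor that is constant within a woman carries no within-woman information about its slope. The fixed intercept is the reference group's follow-up line at month 0 for a woman with average baseline, 1.5·m1 - 0.5·m3, where m1 and m3 are the follow-up means. If the control mean shifts 0.2 SD by month 1 and stays there (assumed), the intercept lies 0.2 SD from the mean baseline.

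**The case against.** The plan never states an intercept-slope covariance. It says that the covariance structure will be examined, allows modifications to improve fit and names AIC. An uncorrelated or intercept-only model is therefore within its terms, and both are identified. This stands: a reader might infer that the specified primary model cannot be fitted, but the documents do not go that far.

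A reader might also infer that the primary test is biased or invalid. It is not, because the marginal covariance and the month-1 contrast remain estimable under any of the equivalent solutions. Nor is a slope variance estimated at zero evidence of harm in itself: if the variances at months 1 and 3 are equal, the uncorrelated model's true slope variance is zero.

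On the choice of model, the first sentence of Aim #1 gives differences at each time point to the linear models, and the primary analysis concerns one time point. In that model the sample-size paragraph's main-effect wording is correct. So the claim that the plan leaves the month-1 test wholly open is too strong. What remains is that no sentence makes the assignment, the missing-data paragraph points to the mixed model, and the two models have different covariate rules. The disagreement rates rest on an assumed share of women seen only at month 3 and on no imputation, although multiple imputation is given as an option.

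Aim 3 is exploratory, its random-slope sentence may be a drafting slip, and no stated test uses the intercept. That limits the weight of that part without making the wording right.

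**Conclusion.** The point holds, at minor to moderate severity. As worded, the growth model asks for slope variation that two follow-ups cannot supply at nominal times if intercept and slope are correlated, and can only just supply if they are not. The consequence is slope variances without a usable meaning and avoidable fitting problems. The primary month-1 contrast is not damaged.

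The more consequential part is the missing designation. Under the natural reading nothing is lost. Under a literal reading of the main-effect wording in the growth model, power falls from 80% to between 41 and 60%, given 105 per arm, a constant 0.5 SD effect and a follow-up correlation of 0.3 to 0.7. The correlation and the constancy of the effect are assumptions. In Aim 3, random slopes for moderators not described as changing within a woman cannot be estimated as within-individual variability. The stated meaning of the intercept is wrong because the responses are follow-up scores.

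**What to change.** - **Aim #1:** replace the random intercept and slope with one repeated-measures model per outcome: categorical time (months 1 and 3), group, group-by-time, baseline, baseline-by-time, unstructured 2x2 covariance, no random effects. Name its month-1 group contrast as the single test at 0.00625, with month 3 secondary. Give one list of adjustment covariates.
- **Sample-size paragraph:** replace the reference to main effects of group with the month-1 group contrast.
- **Aim #3:** use the same model with moderator-by-group-by-time terms and their lower-order terms. Drop the random slopes for time and moderators, and delete the sentence interpreting the intercept.
- **At minimum:** add one sentence naming the model and contrast that give the month-1 test.

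The cost is rewording, with no new data. Two other parts need a consistency check: the Aim #2 mediation plan, which estimates individual slopes and intercepts, and the shared-parameter option in the missing-data paragraph, which may rely on random effects.
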